12. ETHICAL CONSIDERATIONS

12.1 Regulation statement

The trial will be carried out in compliance with the protocol, the ethical principles laid down in the Declaration of Helsinki, in accordance with the ICH Harmonized Tripartite Guideline for GCP, relevant Standard Operating Procedures (SOPs), and relevant regulations.

Standard medical care (prophylactic, diagnostic and therapeutic procedures) remains in the responsibility of the treating physician of the patient.

12.2 Recruitment and consent

Patients will be enrolled to the trial from our center in Canada. Identification of patients eligible for trial participation will occur at two sites, Toronto General Hospital (TGH) and St. Michael's Hospital (SMH) in Toronto, Ontario. Both sites have large, well-established kidney transplant programs (total of 300 to 350 kidney transplants per year and 4000 to 5000 prevalent KTR across both centres). After identification of a patient potentially eligible for the trial, all screening activities and informed consent will take place at TGH. Prior to their visit to the outpatient clinic,

patients will be invited to participate in the study by verbal invitation when they attend the clinic or by sending an invitation letter. In this letter, patients will find a full explanation of the study, advantages and disadvantages of participating, and contact information of the research team members working on this study. Moreover, the letter contains contact information of an independent physician, to whom subjects can address questions about the research before, during and after a study. The patients will be provided with as much time as required to consider their decision and will also be provided with an informed consent form. Participants will be required to sign their written informed consent before they take part in the study.

12.3 Objection by minors or inanticipated subjects (if applicable)

No minors or incapacitated adults will be included in this study.

12.4 Benefits and risks assessment, group relatedness

There are no direct benefits for the patients to be included. Participation in the study is on a freewill base. Patients will receive restitution of all costs of transportation. Patients will not receive priority for treatment of other diseases in the clinic during this study. Participation in the proposed study is accompanied with only minor risks. The blood samples will be drawn by means of venipuncture that will be performed during the visit to the outpatient clinic. All further performed measurements are non-invasive and therefore only minor risks are associated with participation.

12.5 Compensation for injury

The sponsor has an insurance which is in accordance with the legal requirements in Canada. This insurance provides cover for damage to research subjects through injury or death caused by the study.

12.6 Incentives (if applicable)

Participation of patients in the study is a free-will decision. Patients will receive restitution of all costs for transportation for participating. Patients do not receive priority for treatment of other diseases in the clinic during this clinical trial.

13. ADMINISTRATIVE ASPECTS, MONITORING AND PUBLICATION

13.1 Handling and storage of data and documents

A subject identification code list will be made to link the data to the subject in order to be able to trace data to an individual subject. This code will not be based on the patient initials and birth-

date. The key to the code will be safeguarded by the investigator since the data will be kept for a period of 25 years. The handling of personal data will comply with privacy laws, legislation, codes and/or guidelines that apply in the applicable jurisdictions the study is conducted.

13.2 Monitoring and Quality Assurance

The investigator will permit trial-related monitoring, audits, IRB/IEC review, and regulator inspection(s), providing direct access to source data/documents.

13.3 Amendments

A 'substantial amendment' is defined as an amendment to the protocol or any other supporting documentation, that is likely to affect to a significant degree:

- the safety or physical or mental integrity of the subjects of the trial;
- the scientific value of the trial;
- the conduct or management of the trial; or
- the quality or safety of any intervention used in the trial.

All substantial amendments will be notified to the local competent authority.

Non-substantial amendments will be reported to Health Canada as a CTA-Notification, or to the local competent health authority as appropriate as per the jurisdiction.

Non-substantial amendments will not be notified to the competent authority, but will be recorded and filed by the sponsor.

13.4 Annual progress report

The sponsor/investigator will submit a summary of the progress of the trial to the REB as part of the annual renewal process. Information will be provided on the date of inclusion of the first subject, numbers of subjects included and numbers of subjects that have completed the trial, serious adverse events/ serious adverse reactions, other problems, and amendments.

13.5 Public disclosure and publication policy

The study will be registered at clinicaltrials.gov or equivalent trial registries. Publication policy is in agreement with international regulations. Nor the sponsors, nor the principal investigator has a right of veto regarding the way of publishing the results.

95. [name] DZ, Miller JA, Scholey JW, Bradley TJ, Slorach C, Curtis JR, Dekker MG, Nasrallah R, Hebert RL and Sochett EB. The effect of cyclooxygenase-2 inhibition on renal hemodynamic function in humans with type 1 diabetes. *Diabetes*. 2008;57:688-95.

96. [name] DZ, Sochett EB, Lai V, Dekker MG, Slorach C, Scholey JW and Bradley TJ. Renal hyperfiltration and arterial stiffness in humans with uncomplicated type 1 diabetes. *Diabetes care*. 2010;33:2068-70.

15. Tables and Figures.

Figure 1: Effects of SGLT2 inhibition on the nephron.

Figure reproduced from: van Bommel EJ. Et al. SGLT2 Inhibition in the Diabetic Kidney-From Mechanisms to Clinical Outcome. *Clin J Am Soc Nephrol*. 2017;12:700-710.

[figure not shown]

Figure 2: Potential cardio- and renoprotective mechanisms of SGLT2 inhibition.

Figure reproduced from: Heerspink HJ. et al. Sodium Glucose Cotransporter 2 Inhibitors in the Treatment of Diabetes Mellitus: Cardiovascular and Kidney Effects, Potential Mechanisms, and Clinical Applications. *Circulation*. 2016;134:752-72.

[figure not shown]

Figure 3: Study design

Continuation of existing therapy including immunosuppression, anti-hypertensives, glycemic medications

			1		
SCREENING Visit 1	BASELINE Visit 2 Visit 3	WEEK 1 ACUTE Visit 4	DOSING Visit 5 Visit 6 Visit 7	WEEK 12 CHRONIC Visit 8 Visit 9	Follow UP Visit 10

Observational	Observational studies							
Author, Year	Participants	Design	Treatment	Results				
Rajasekeran et al. Diabetes Care 2017 ¹ Mahling et al.	N=10 KTR & SPKTR with PTDM or T2D N=10 KTR with	Observational cohort study, 80.5 person- months follow- up Observational	canagliflozin	Weight, kg: -2.14 (SD 2.8) Systolic blood pressure, mmHg: -6.5 (SD 10.8) Diastolic blood pressure, mmHg: -4.8 (SD 12) Serum creatinine, mmol/L: 9.7 (SD 14.6); eGFR, mL/min/1.73 ² : -4.3 (SD 12.2) No urinary/mycotic infections, AKI or acute rejection Weight, kg: -1.9 (-1.9 to 0.1)				
Kidney Blood Press Res 2019 ²	PTDM or T2D	study, 6.3 person-years		Systolic blood pressure, mmHg: -2.5 (-36.3 to 0.8) Diastolic blood pressure, mmHg: -0.5 (-9.5 to 7.5) 2 episodes of UTI, 1 episode of AKI				
Alkindi et al. Transplant Proc 2020 ³	N=8 KTR with PTDM or T2D	Retrospective chart review	empagliflozin (6 patients), dapagliflozin (2 patients)	BMI , kg/m ² , 32.7 \pm 7.2 to 27.4 \pm 4.2 after 12 months (p<0.05) Systolic blood pressure , mmHg: 135 \pm 9.6 to 126.4 \pm 11.5 after 12 months (p>0.05) Diastolic blood pressure , mmHg: 80.6 \pm 10 to 74.5 \pm 7.3 after 12 months (p>0.05) eGFR , no significant change 1 episode of UTI, no AKI, ketoacidosis, acute rejection				
Schwaiger et al. AJT 2018 ⁴	N=14 KTR with PTDM, 6 months post-transplant, eGFR \geq 30ml/min/1.73m ² , stable on insulin therapy	Open-label, single-arm, non- inferiority study Single-centre study	Treatment with empagliflozin 10mg after discontinuation of insulin therapy, 4 weeks	Change in baseline to 4 week OGTT - fasting and 2-hour glucose levels increased to $144 \pm 45 \text{ mg/dL}$ (P = .005) and $273 \pm 116 \text{ mg/dL}$ (P = .06), respectively Avg body weight: -1.6kg; Bioimpedance volume status: fluid overload decreased from 2.7 ± 2.1 (baseline) to 1.8 $\pm 1.8L$ (P = .006) 5 episodes of urinary tract infection				
Randomized C		Γ	Γ					
Author, Year	Participants	Design	Treatment	Results				

Table 1: Summary	v of studies of SGLT2i in kidney	y trans	plant reci	pients.
Observational st	-diag			

Halden et al.	N=49 KTR with	Double-blind	1:1	Secondary Outcomes
Diabetes	PTDM, 1 year post	RCT	empagliflozin	Change in median HbA1c (%): -0.2 (-0.6 to -0.1) with
Care ⁵	transplant, eGFR	Single centre	10mg vs.	empagliflozin vs +0.1 (-0.1 to 0.4); p=0.025
	\geq 30m/min/1.73m ²	study	placebo, 24	Body Weight : -2.5 kg (-4.0 to -0.05) with empagliflozin
			weeks	vs +1.0 kg (0.0 to 2.0); p=0.014
				24hr blood pressure – no difference in blood pressure
				between groups
				Safety Outcomes – no significant between group
				differences

KTR: Kidney transplant recipients; SPKTR: Simultaneous pancreas-kidney transplant recipients; T2D: Type 2 diabetes; PTDM: Post-transplant diabetes mellitus; eGFR: Estimated glomerular filtration rate; SD: Standard deviation. OGTT: Oral Glucose Tolerance Test

hyperfiltration). This has also been part of previous mechanistic studies in the [name] Laboratory in patients with diabetes. ^bIn patients with T2D/PTDM ^c Renal ultrasound will be performed between visits 2 and 3 and between visits 8 and 9. ^c Lithium tablet will be taken at 10pm the night before Visits 3,4 and 9. *Study visits are subject to PI's discretion based on participants' condition/safety/lab results. HGM; home glucose monitoring; NICOM; Non-invasive cardiac output monitoring; EEOS; early end of study

Table 3:	Study variables	included in	data collection
----------	-----------------	-------------	-----------------

Category	Demographic &	Imaging	Physical	Adverse events	Laboratory	Laboratory
	medical history		examination		(Blood)	(Urine)
Category Variables	0 1	Imaging Tissue hypoxia ultrasound of allograft	-	Adverse events Hypotension, volume depletion, Hyper-kalemia, acute kidney injury, urinary infections, mycotic infections, amputation, allergic reaction, hypo-glycaemia, ketoacidosis	· ·	v
	history				cholesterol profile, CNI level, beta-HCG	
					catecholamines	

	Heart rate variability Arterial stiff- ness, aortic pulse wave velocity, cardiac output, stroke volume, total peripheral resistance	Death-censored graft failure, death with graft function, biopsy- proven acute rejection	Biomarker biobanking GFR (iohexol), 8-hydroxy- deoxyguanosine, 8-isoprostane	8-hydroxy- deoxyguanosine, 8-isoprostane, urine adenosine, biomarker biobanking

ESRD: End-stage renal disease; RRT: Renal replacement therapy; GFR: Glomerular filtration rate.

## **INFINITI Data Analysis Plan**

## **Objectives**

## 1. Primary objective:

The primary objective is to determine if acute and chronic dapagliflozin use causes a change in systolic blood pressure compared to placebo. Acute means changes from baseline to Visit 4 (1 week), and chronic means changes from baseline to Visit 9 (12 weeks).

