## **INFINITI Data Analysis Plan**

## **Outcomes**

### 1. Outcomes for the primary objective:

- 1.1. The primary outcome is measured by the acute and chronic change in seated systolic blood pressure (measured using automated sphygmomanometer) from baseline with dapagliflozin vs placebo.
- 1.2. We will also measure the primary objective on these secondary outcomes:
  - a. Seated diastolic blood pressure
  - b. Seated mean arterial pressure

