# 1. Analysis for the primary objective:

- 1.1. To assess dapagliflozin-related acute and chronic changes in the primary outcome of seated systolic blood pressure compared to placebo, linear mixed-effects models will be used. Two separate models will be fit. For acute change, the vector of outcomes will include the baseline and 1-week values (i.e. Visit 3 and Visit 4 values). For chronic changes, the vector of outcomes will include the baseline and 12-week values (i.e. Visit 3 and Visit 9 values). The covariates will include the visit and treatment-by-visit interaction; due to randomization, a covariate for the main effect of treatment will not be included. The treatment-by-time coefficient, its 95% confidence interval, and its p-value will be used to assess the effect of treatment.
- 1.2. We will repeat this analysis with:
  - a. Seated diastolic blood pressure as an outcome
  - b. Seated mean arterial pressure as an outcome

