#### 5. Pre-specified post-hoc analyses:

- 5.1. The same models described in the analysis of primary objective 1.1 will be performed for the outcome.
- 5.2. The same models described in the analysis of exploratory objective 3.2 will be completed for each of the different outcomes.

Analysis population: The intention to treat population will be used for all analyses.

*Hypothesis testing:* For hypothesis testing, a 5% significance level will be used (two-sided). No interim analyses will be performed. For secondary objectives, nominal p-values will be reported.

*General model assumptions and model diagnostic procedures:* For the linear mixed-effects models with visit and treatment-by-visit interaction as covariates, a participant-level random intercept will be included. Restricted-maximum-likelihood will be used for estimation and the missing-at-random framework will be assumed. Plots of marginal and conditional residuals will be used for model diagnostics and assessment. Similar diagnostic procedures will be used for the linear regression models.

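### The SAP makes the 1-week and the 12-week SBP change both primary, each at an unsplit two-sided 5% and with no success rule, while the protocol names 12 weeks only and is sized for one test

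*SAP*

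**What the plan says.** **SAP.** The primary objective reads: "The primary objective is to determine if acute and chronic dapagliflozin use causes a change in systolic blood pressure compared to placebo". The same paragraph defines acute as baseline to Visit 4 (week 1) and chronic as baseline to Visit 9 (week 12). Outcome 1.1 repeats the pairing: "The primary outcome is measured by the acute and chronic change in seated systolic blood pressure". In Analysis 1.1, "Two separate models will be fit", one on Visits 3 and 4 and one on Visits 3 and 9. For each, "The treatment-by-time coefficient, its 95% confidence interval, and its p-value will be used to assess the effect of treatment". The closing paragraph on hypothesis testing sets one two-sided 5% level and rules out interim analyses. Its only remark on multiple results is "For secondary objectives, nominal p-values will be reported". It does not say how the two primary p-values are to be combined.

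**Protocol.** Section 3.1 gives the primary objective as the effect of 12 weeks of treatment on systolic pressure. Section 11 defines the primary outcome as the between-group difference in blood pressure reduction at 12 weeks. Section 5.3 sizes the trial for a single comparison: 6.5 mmHg, SD 8 mmHg, two-sided 0.05, 80% power, 24 per arm, raised to 52 in total for 10% attrition.

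**The concern.** There are two primary contrasts, two p-values and no rule linking them. A significant 1-week result with a non-significant 12-week result, or the reverse, could be reported as meeting or missing the primary objective, depending on which document is followed and which rule is adopted afterwards.

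The two natural rules fail in different ways. If significance at either visit is enough, two tests at 5% give an overall error above 5%. If significance at both is needed, the error is controlled, but the chance of success is lower than for the single test on which the sample size rests. The label on secondary p-values does not help, because the 1-week change is listed as primary.

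**Working it through.** **Step 1: reproduce the planned size.** Inputs from Protocol 5.3: difference 6.5, SD 8, two-sided alpha 0.05, power 0.80, 1:1 allocation.

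n per arm = 2 × 8² × (1.960 + 0.842)² / 6.5² = 23.8, rounded up to 24, or 48 in total. This matches the protocol. The noncentrality is 6.5 / (8 × √(2/24)) = 2.815, and power = Φ(2.815 − 1.960) = 80.4%. The stated size is therefore that of one test, with no allowance for a second.

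**Step 2: correlation between the two tests.** Both models use the same participants and the same baseline visit, so the tests are correlated. The documents give no correlation. In the SAP's models the baseline means are held equal ("due to randomization, a covariate for the main effect of treatment will not be included") and each participant has a random intercept. Assume SBP has the same correlation r between any two visits, and read SD 8 as the SD of change. Then:

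- effective SD of the treatment contrast = 8 × √((1 + r)/2)
- correlation between the two tests, ρ = r/(1 + r)

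Test correlations of 0.5 to 0.9 are also shown, without reference to that model.

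**Step 3: error if either visit counts.** Under no effect, error = 1 − P(|Z₁| < 1.96 and |Z₂| < 1.96), with bivariate normal statistics. False benefit counts only errors in favour of dapagliflozin; its reference value is 2.5%.

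| Assumption | ρ | Either-visit error | False benefit |
|---|---|---|---|
| Independent tests | 0 | 9.75% | 4.9% |
| SAP model, r = 0.4 | 0.29 | 9.5% | 4.8% |
| SAP model, r = 0.6 | 0.38 | 9.4% | 4.7% |
| SAP model, r = 0.8 | 0.44 | 9.2% | 4.6% |
| Test correlation 0.5 | 0.5 | 9.1% | 4.5% |
| Test correlation 0.8 | 0.8 | 7.8% | 3.9% |
| Test correlation 0.9 | 0.9 | 7.0% | 3.5% |

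Every assumed value exceeds 5%.

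**Step 4: power if both visits are required.** Power = P(Z₁ > 1.96 and Z₂ > 1.96), assuming a true effect of 6.5 mmHg at each visit. Protocol 5.3 gives one effect and no time point, so the 1-week value is an assumption.

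- *Protocol's unadjusted calculation, 24 per arm:* single test 80.4%; both 69.2%, 73.3% and 75.4% at ρ = 0.5, 0.8 and 0.9.
- *SAP model, 24 per arm:*

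| r | Effective SD | Single 12-week test | Both visits |
|---|---|---|---|
| 0.4 | 6.69 | 92.0% | 85.4% |
| 0.5 | 6.93 | 90.1% | 82.6% |
| 0.6 | 7.16 | 88.2% | 79.7% |
| 0.7 | 7.38 | 86.3% | 76.9% |
| 0.8 | 7.59 | 84.3% | 74.3% |

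If all 52 participants provide data (26 per arm, the best case), the unadjusted single-test power is 83.4% and both-visits power 73.5% to 78.9% (ρ = 0.5 to 0.9). Under the SAP model, both-visits power is 88.6% to 78.3%, against 93.8% to 87.0% for the single test.

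**Step 5: check without the normal approximation.** A t-based ANCOVA simulation standing in for the SAP's model (50,000 trials per setting) gives either-visit error of 9.2% to 9.7%. At 24 per arm, both-visits power is 82.8% to 70.6%, against 90.5% to 81.7% for the single test. The loss is about 8 to 11 points, slightly more than in Step 4.

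**Step 6: smaller 1-week effect.** Under the Step 4 SAP model at 24 per arm, with 6.5 mmHg kept at week 12, both-visits power is about 69% to 57% if the 1-week effect is 5 mmHg, and about 52% to 42% if it is 4 mmHg.

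**The case against.** The strongest reply is that the SAP never says either visit suffices. It joins acute and chronic with an and, and if both are required the error does not exceed 5%. The inflated figures then belong to a rule the SAP does not state. The chronic model also yields the 12-week estimate with its own interval and p-value, so the protocol's primary test can be reported at 5% whether or not the SAP is edited. The protocol is itself loose in places: section 9.1.1 lists five measurement days without naming a primary one, and section 3.1 can be read as giving treatment duration. Section 7.6.3 describes the study as mechanistic, so a labelling slip may seem minor.

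Some of this stands. The inflation is conditional on an either-visit rule and should be presented that way. Section 11 is the protocol's one explicit time point for the primary outcome, with section 3.1 consistent with it. The power under a both-visits rule also depends on an unsupported 1-week effect, though a smaller effect only raises the cost of that rule.

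The defect remains. If the conjunctive wording is taken as the rule, the trial has a joint requirement it was not sized for, and one that contradicts protocol section 11. If it is not, no rule exists. Neither document says which prevails, and the primary result is where this matters most.

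**Conclusion.** The point holds and should be fixed. The two documents disagree on the primary outcome, and the SAP leaves the success criterion open.

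An either-visit rule would roughly double the nominal 5% error under the SAP's model, assuming equal correlation of 0.4 to 0.8 between visits, and would still exceed 5% at the higher test correlations tried. A both-visits rule would control the error but cost about 7 to 10 points of power at 24 per arm by the normal calculation, or 8 to 11 by simulation. It could stay near 80%, but only if the 1-week effect is as large as the 12-week effect. A single 12-week test keeps 5% error and the planned power.

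That the mismatch exists and the rule is missing rests on the text alone. Only the sizes depend on the assumed correlations, the reading of SD 8 and the 1-week effect.

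**What to change.** In SAP Objective 1, Outcome 1.1 and Analysis 1.1, name the Visit 3 to Visit 9 change in seated SBP as the sole primary outcome, tested at two-sided 5%. This matches protocol sections 3.1, 5.3 and 11. Move the Visit 3 to Visit 4 change to the secondary objectives with a nominal p-value. If an error-controlled 1-week claim is wanted, state instead that it is tested second in a fixed sequence at two-sided 5%, only if the 12-week test is significant. Make the change before unblinding; the documents do not say whether that has happened.

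The cost is SAP wording and the loss of stand-alone primary status for the 1-week result. Models, data collection and sample size are unchanged.

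Keeping both as primary costs more. Requiring both brings the power loss above. Allowing either with alpha split to 0.025 each needs 29 per arm by the protocol's method, or 58 in total and 65 after 10% attrition (58/0.9 = 64.4, rounded up). At 24 per arm the split leaves 71.7% power per test.

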## 2. Secondary objectives:

2.1. We will characterize the safety of dapagliflozin use compared to placebo.

We will determine acute and chronic effects of dapagliflozin vs. placebo from baseline on:

- 2.2. Calcineurin inhibitors (CNI) levels, a class of immunosuppressants measured by tacrolimus or cyclosporine
- 2.3. Systemic hemodynamics
- 2.4. Total and proximal renal tubular natriuresis measured by sodium/lithium clearance
- 2.5. Sympathetic nervous system (SNS) activation
- 2.6. Metabolic parameters
- 2.7. Kidney function indicated by iohexol-measured and estimated glomerular filtration rate (GFR)
- 2.8. Neurohormones
- 2.9. Glucose-lowering effects

### 3. Exploratory objectives:

- 3.1. We will determine acute and chronic effects of dapagliflozin vs. placebo from baseline on estimated plasma volume (ePV).
- 3.2. We will assess whether the proximal renal tubular natriuretic effect of dapagliflozin leads to volume contraction compared to placebo. To this end, we will determine the association between acute and chronic changes to fractional sodium handling and acute and chronic changes in volume markers.
- 3.3. We will assess whether the proximal renal tubular natriuretic effect of dapagliflozin is associated with changes in kidney function compared to placebo. To this end, we will determine the association between acute and chronic changes to fractional sodium handling and acute and chronic changes in GFR.
- 3.4. We will assess whether volume contraction with dapagliflozin leads is associated with SNS activation compared to placebo. To this end, we will determine the association between acute and chronic changes to volume markers and acute and chronic changes in markers of SNS activation.
- 3.5. We will determine whether changes in neurohormones and volume markers are associated with changes in kidney function. To this end, we will determine the

association between acute and chronic changes in absolute measures of kidney function and the acute and chronic changes in neurohormones and volume markers with dapagliflozin compared to placebo.

- 3.6. We will determine whether changes in neuro-hemodynamic & volume markers are associated with changes in arterial stiffness. To this end, we will determine the association between acute and chronic changes in arterial stiffness and the corresponding acute and chronic changes in neurohormones and volume markers with dapagliflozin compared to placebo.
- 3.7. We will determine whether changes in neurohormones and volume markers are associated with changes in blood pressure. To this end, we will determine the association between acute and chronic changes in blood pressure and the acute chronic changes in neurohormones and volume markers with dapagliflozin compared to placebo.
- 3.8. We will determine acute and chronic effects of dapagliflozin vs. placebo from baseline on urine and plasma chemistry marker levels.

